17.0 References

PROSPECTIVE EVALUATION OF CYBERKNIFE STEREOTACTIC RADIOSURGERY FOR LOW AND INTERMEDIATE RISK PROSTATE CANCER: EMULATING HDR BRACHYTHERAPY DOSIMETRY

SCHEMA

PATIENT POPULATION (see section 4.0 for complete eligibility)

Histologically-confirmed, adenocarcinoma of the prostate

Clinical Stage T1b - T2b, NX-0, MX-0

One of the following combinations:

- Gleason score 2-6 and PSA 20
- Gleason score 7 and PSA 10

ECOG Performance Status 0-1

No prior prostate radiation or other definitive therapy

Required sample size: 253

ELIGIBILITY CHECKLIST

(Y)	Is there histologically proven prostate adenocarcinoma, biopsy within one year of enrollment?
(2-6)	What is the Gleason Score?
(T1b - T2b)	What is the clinical T-stage? (AJCC 6 th Edition)
(Y)	Is the patient clinical Nx or N0, and Mx or M0?
(0-20)	What is the patient's PSA?
(L, I)	Does the patient fall into one of these risk groups (AJCC 6 th Edition): - Low: CS T1b-T2a, Gleason 2-6, PSA 10 - Intermediate: CS T2b, Gleason 2-6, PSA 10, or CS T1b-T2a, and Gleason 2-6, PSA 20 ng/ml, or Gleason 7, PSA 10 ng/ml
(0-1)	What is the ECOG performance status?
(N)	Has the patient undergone prostatectomy or cryotherapy of the prostate?
(N)	Has the patient had radiotherapy to the prostate or lower pelvis?
(N)	Is there implanted hardware near the planning target volume that would prohibit appropriate treatment planning or treatment delivery in the investigator's opinion?
(N)	Has the patient had chemotherapy for a malignancy in the last 5 years?
(N)	Has the patient had an invasive malignancy (other than this prostate cancer, or basal or squamous skin cancers) in the last 5 years?
(N)	Has the patient's androgen function been ablated during the past 2 months?

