4. PRETREATMENT EVALUATION

- 4.1. Complete history and physical exam
- 4.2. DRE findings
- 4.3. Assessment of performance status
- 4.4. Histological evaluation of prostate biopsy with assignment of Gleason score
- 4.5. Evaluation of the pelvic lymph nodes with CT or MRI is optional
- 4.6. Serum PSA. Laboratory evaluation must be done within 90 days prior to registration, or <60 days prior to hormone therapy, and 30 or 90 days after discontinuing finasteride or dutasteride, respectively.
- 4.7. CBC, platelets, serum BUN, creatinine and testosterone; may be drawn after registration
- 4.8. Transrectal ultrasound volume study of the prostate or a digital rectal exam (DRE) will be performed prior to enrollment to verify the prostate volume. The prostate volume may be obtained by step section summated measurements at 5 mm intervals through the entire gland (stepping method) or the by the length-width-height method. An MRI-based prostate volume measurement will also be acceptable (specify which modality).
 - 4.8.1. Measurement from CT or ultrasound 6 months prior to registration, or 14 days prior to registration if hormone therapy given; if patient had taken finasteride or dutasteride, volume determined >30 or >90 days (respectively) after discontinuation.
- 4.9. Patient should be able to complete questionnaires (see Appendix VI), baseline questionnaires may be completed before or after enrollment, but before treatment)
 - 4.9.1. SF-12 questionnaire
 - 4.9.2. AUA questionnaire
 - 4.9.3. EPIC-26 questionnaire
 - 4.9.4. SHIM questionnaire
 - 4.9.5. Utilization of Sexual Medications/Devices questionnaire

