- 5.13. No hormone ablation for two months prior to enrollment, or during treatment. This includes LHRH agonists (e.g. leuprolide,goserelin, triptorelin) and antagonists (e.g. degarelix), peripheral blockers (e.g. flutamide, bicalutamide, nilutamide), estrogens (e.g. DES), bilateral orchiectomy, and 5-alpha reductase inhibitors (finasteride or dutasteride).
- 5.14. Completion of patient questionnaires in section 4.7.
- 5.15. Consent signed.

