9.1. EVALUATION DURING TREATMENT & FOLLOWING TREATMENT

- 9.1.1. PRE-ENTRY ASSESSMENT: see section 4.7.
- 9.1.2. Stereotactic radiosurgery is an outpatient procedure. Patient management immediately after the procedure will follow routine patient care guidelines as determined by the physician. Subjects will be provided instructions on who to call with specific contact information, in the event they experience any untoward effects following treatment. In the event a subject experiences any untoward effects following CyberKnife treatment, information specific to the patient's condition and symptoms, treatment intervention required, and hospital stay and course will be recorded for purposes of clinical evaluation.
- 9.1.3. ACUTE ASSESSMENT: Patients will have toxicity evaluation and AUA score on the last day of treatment.
- 9.1.4. ASSESSMENTS FOLLOWING TREATMENT: at one week after treatment (allowed window: +/- 3 days), toxicity and AUA score will be evaluated. At 1 month (+/- 7 days) following treatment, patients will be assessed for acute toxicity, and will fill out AUA form, SF-12, EPIC-26, SHIM and Utilization of Sexual Rx/Devices. At 3, 6, 12, 18, and 24 month (+/- 2 wks) intervals (and every 6 months thereafter, through year 5), patients will be seen and evaluated, including a history, physical exam, ECOG performance status, PSA, toxicity evaluation, and AUA score. In addition, at 6 months, 12 months and annually thereafter, the SF-12, EPIC-26, SHIM and Utilization of Sexual Medications/Devices will be administered. After the 5 year follow-up patients will be seen yearly through year 10 (allowed window: +/-1 month) and the following will be performed: PSA, toxicity evaluation, and the following questionnaires will be administered: EPIC -26; AUA; SHIM. Examination and studies may

- be done at outside facility. A serum total testosterone will be measured at baseline and with every PSA through year 2.
- 9.1.5. PROSTATE BIOPSY will be performed at time of biochemical or local clinical failure, and is encouraged at 2 years following treatment and at time of distant failure.
- 9.1.6. BONE SCAN will be performed at the time of biochemical failure, or when the patient develops signs of symptoms suggesting metastatic disease.
- 9.1.7. Axial Imaging (CT or MRI) of the abdomen and pelvis will be performed at the time of biochemical failure, or when the patient develops signs of symptoms suggesting metastatic disease.

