11.4.2. SECONDARY OBJECTIVES

1. Local and Distant Tumor Control

As defined in Section 9.4, the failure to achieve local and distant tumor control will be documented for each patient. These rates will be summarized and descriptive statistics (standard deviations, confidence intervals) will calculated.

2. Quality of Life Assessments

The SF-12 total score, AUA score, EPIC-26 total score and the EPIC-sexual domain sub score are used to quantify quality of life (QoL) at baseline and repeatedly during the post treatment period (see Section 9.0). We will use the generalized estimating equation (GEE) method to provide valid inferences. This method was originated to make inference about average behavior, where the dependent variable depends not only on the "explanatory" variable (time measured in months) but also on the correlation of a patient's repeated measurements. The GEE approach fits the model to the observed data as closely as possible, weighting each patients' "cluster" of measurements over time inversely to its variance - covariance matrix. With this method, no imputations are required and all data recorded is use in the analysis. Other important features of GEE are that no distributional assumptions for the dependent variable are required to use the method and in most cases valid inferences are provided even when the correlation structure is miss-specified. For each score, we will use GEE to fit a straight line to patients' longitudinal course of repeated values. We hypothesize that immediately following treatment, the GU & GI subsections of the EPIC-26 and the AUA will demonstrate a worsening of GU and GI function, but this will return to normal with time. We further hypothesize that the sexual function subset of the EPIC-26 will show gradual worsening function relative to baseline over the five-year follow-up period. These QOL outcomes will be compared to those reported in other prospective studies using the same instruments, including RTOG 0232

and 0415. We hypothesize that the slope of a fitted line will not be significantly less than zero; that is, QoL will be maintained throughout the assessment period.

3. Adverse Events

All adverse events will be recorded on the case report forms. For both acute (<=90 days of treatment start) and late (>90 days of treatment start), the frequency and proportion of each type of adverse event will be presented in tabular form, on both a per-patient and a per-event basis.

4. Survival

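### With a two-month hormone washout and no testosterone entry test, recovery could tilt the EPIC sexual slope upward; the size is unknown and no planned QoL analysis checks for it

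*Combined protocol and SAP*

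**What the plan says.** - **Entry.** Section 5.13 requires "No hormone ablation for two months prior to enrollment, or during treatment". It lists LHRH agonists and antagonists, peripheral blockers, estrogens, orchiectomy and 5-alpha reductase inhibitors together, and sets no limit on use before that window. The Eligibility Checklist asks "Has the patient's androgen function been ablated during the past 2 months" and requires the answer no.
- **Earlier hormone therapy is foreseen.** Section 4.6 times the PSA relative to it. Section 4.8.1 sets the volume measurement at "or 14 days prior to registration if hormone therapy given".
- **Testosterone.** Section 4.7 lists "CBC, platelets, serum BUN, creatinine and testosterone; may be drawn after registration", so the result cannot decide entry. Section 9.1.4 adds "A serum total testosterone will be measured at baseline and with every PSA through year 2".
- **Baseline scores.** Section 4.9 says "baseline questionnaires may be completed before or after enrollment, but before treatment".
- **Analysis.** In 11.4.2, "we will use GEE to fit a straight line to" each patient's repeated scores, with time in months as the explanatory variable. The analysed scores include the EPIC-26 total and the EPIC sexual subscore. The plan expects a slope that is not significantly negative and reads that as QoL being maintained. The same section also predicts that the "sexual function subset of the EPIC-26 will show gradual worsening function relative to baseline" over five years.
- Section 11 does not mention testosterone or prior hormone therapy.

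**The concern.** A slope over time shows the effect of treatment only if the starting level is stable. If a man's sexual function, energy or hot flashes at baseline still reflect an earlier drug, his scores rise as the drug effect fades, whatever CyberKnife does. The trial has one arm, so no concurrent control cancels that rise. The QoL criterion is one of non-significance in the downward direction, so an upward drift makes it easier to meet. What is at stake is a secondary claim, that QoL is maintained, for the EPIC sexual score and to a lesser degree the EPIC-26 total. The primary bDFS and toxicity analyses are not touched. SHIM is collected but is not among the scores named for the GEE analysis.

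**Working it through.** **1. The plan's own figure.** The QoL analysis has no sample-size calculation, so I take n from 11.3. Formula 1 with π0 = 0.90, π1 = 0.945, z = 1.645 and 0.84:

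N = [0.84·√(0.945·0.055) + 1.645·√(0.90·0.10)]² / 0.045² = (0.1915 + 0.4935)² / 0.002025 = 231.7, so 232. Then 232/0.92 = 252.2, so 253. Both figures reproduce. I use n = 232.

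**2. Bias in the slope.** EPIC-26 is given at 0, 1, 6, 12, 24, 36, 48 and 60 months (9.1.4). Mean time is 187/8 = 23.375 months, and Sxx = 7957 − 8·23.375² = 3585.9. With complete data, GEE with an independence or exchangeable working correlation gives the least-squares slope.

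Let a share f of men be d points low on the day of the baseline questionnaire and recover linearly by month R. The mean shift at month t is −f·d·max(0, 1 − t/R).

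- R = 12: (23.375·1 + 22.375·0.9167 + 17.375·0.5)/3585.9 = 0.01466 per month, or 0.176·f·d points/year
- R = 24: (23.375·1 + 22.375·0.9583 + 17.375·0.75 + 11.375·0.5)/3585.9 = 0.01772 per month, or 0.213·f·d points/year

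The documents give no value for f, d or R. Assumed range: f 5-20%, d 15-25 points, R 12-24 months.

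| f, d | f·d | R = 12 | R = 24 |
|---|---|---|---|
| 5%, 15 | 0.75 | +0.13/yr | +0.16/yr |
| 10%, 25 | 2.5 | +0.44/yr | +0.53/yr |
| 20%, 25 | 5.0 | +0.88/yr | +1.06/yr |

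**3. Standard error.** SE = 12·√[SD²(1 − ρ)/(Sxx·232)]. SD and ρ are also assumed.

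- SD 20, ρ 0.7: 12·√(120/831,923) = 0.14/yr
- SD 25, ρ 0.6: 12·√(250/831,923) = 0.21/yr
- SD 30, ρ 0.5: 12·√(450/831,923) = 0.28/yr

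**4. Comparison.** At the low corner the bias (0.13) is below one SE anywhere in that range. At 10%, 25 points and 12 months it is 0.44/0.21, about 2 SE. With 1% of men and 20 points it would be 0.01·20·0.176 = 0.035/yr, which is negligible.

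**5. Effect on the test.** Section 11.4.2 gives no significance level for the slope, so I borrow the one-sided 5% of the primary endpoint. Power = Φ[(decline − bias)/SE − 1.645], with SE 0.208/yr.

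- True decline 0.75/yr: 97.5% without bias; 61% with 10%, 20 points, 12 months (bias 0.35); 44% with 10%, 25 points, 12 months (bias 0.44)
- True decline of 5 points over 60 months: 99.9% without bias; 89% with a 2-point bias
- True decline of 8 points over 60 months: still 98.6% with a 4-point bias

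A moderate decline could thus be partly masked, while a large one would still show. I give no figure for the EPIC-26 total: its urinary and bowel items dilute the effect, and the plan does not say how the total is scored.

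**The case against.** Several points on the other side have weight.

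- **Checklist wording.** It asks whether androgen function was ablated, not when the last dose was given. Read literally, a man still suppressed by a depot drug is ineligible. A reader might infer from 5.13 that suppressed men are knowingly admitted; the documents do not say that. What stands is that no laboratory value backs the checklist answer.
- **Timing.** Treatment may start up to 90 days after registration (6.2), so a baseline questionnaire can fall about five months after last use even for a man who only just met the washout. Biopsy must be within a year (5.2.2), so without a repeat biopsy, hormones begun after diagnosis ran at most about 10 months. Both shrink the likely deficit. However, 4.9 also allows the questionnaire before enrollment, so baseline is not tied to the end of the washout.
- **Direction.** A reader might infer that the bias favours every QoL hypothesis. It does not: it works against the prediction of gradual sexual worsening and favours only the general expectation that slopes are not significantly negative. Those two statements in 11.4.2 conflict for the sexual score and need reconciling separately.
- **Unused testosterone.** Collecting a laboratory value without modelling it is not an error. It follows the PSA schedule, and the 1-month EPIC visit has none. It matters here only because the baseline value could show whether the problem exists.
- **Magnitude.** Every input to the size is assumed, and the 2-SE example uses the largest assumed deficit.

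**Conclusion.** The gap is real but modest. The entry rules do not ensure hormonal recovery at baseline, the QoL model has no hormonal term, and any recovery would tilt the EPIC sexual slope upward under a criterion that such a tilt helps to satisfy. Under the assumed values the bias is 0.13-1.06 points/year against an SE of 0.14-0.28, and it is negligible if few men had recent deprivation. The documents do not support the stronger inference that recovery will hide a CyberKnife-related decline or that the planned QoL conclusion is invalid: the share of affected men, their deficit and their recovery time are all unstated. They do support adding a pre-specified check. They do not support replacing the all-patient slope with a subgroup slope as the main result.

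**What to change.** Leave the entry rule and the planned all-patient slope as they are, and add to 11.4.2:

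1. For the EPIC sexual score and the EPIC-26 total, a supporting GEE model with an indicator for baseline testosterone below the laboratory's normal range **and** its interaction with time. The indicator alone would not help, because the bias is in the slope.
2. Report the slope in men with normal baseline testosterone beside the overall slope, both with confidence intervals, and the number of men in each group. State that QoL is maintained only if both slopes lead to that conclusion. The intervals matter because non-significance is easier to reach with fewer men.
3. Where earlier LHRH-agonist, LHRH-antagonist or anti-androgen use is recorded, repeat the analysis by that history. Leave 5-alpha reductase inhibitors out of the definition, although 5.13 groups them with the others.
4. Use baseline testosterone, not later values, which treatment could affect; 8.3.4.9 already records dose to the testes.

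**Cost.** Items 1, 2 and 4 need only SAP wording, since baseline testosterone is already collected. Item 3 depends on what the case report forms hold: eligibility asks only about the last two months, and the forms are not reproduced in the protocol. The downside is one extra analysis of secondary outcomes, with slightly fewer men in the restricted slope. Low testosterone is also an imperfect marker, because it includes men whose low level has nothing to do with earlier drugs. That is a further reason to keep this analysis supporting.

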9.2. CRITERIA FOR TOXICITY

- 9.2.1. ACUTE AND LATE TOXICITY
- 9.2.2. Acute side effects (<=90 days of treatment start) will be assessed using the NCI Common Toxicity Criteria version 3.0 (see appendix V).

9.3. QUALITY OF LIFE ASSESSMENTS

- 9.3.1. SF-12: The SHORT FORM-12 Health Survey measures generic health status relevant across different age, disease, and treatment groups. It provides a comprehensive, psychometrically sound assessment of health status from the patient's point of view by scoring responses to standard questions. The SF-12 is self-administered, and can usually be completed in less than 3 minutes without assistance.
- 9.3.2. EXPANDED PROSTATE CANCER INDEX COMPOSITE (EPIC)-26: is a validated comprehensive instrument developed to assess patient function and bother after prostate cancer treatment. It was developed by an expert panel of urological oncologists, radiation oncologists (including those with brachytherapy expertise), survey researchers, and prostate cancer nurses, to address symptoms related to radical prostatectomy, external beam radiotherapy, prostate brachytherapy, and hormonal symptoms. See appendix VI.
- 9.3.3. AMERICAN UROLOGICAL ASSOCIATION (AUA) SYMPTOM INDEX: Also known as the International Prostate Symptom Score (IPSS), this widely used index assesses urinary symptom bother. See appendix VI.
- 9.3.4. SEXUAL HEALTH INVENTORY FOR MEN (SHIM): is a widely used, internationally validated and sensitive instrument for assessing erectile dysfunction¹.
- 9.3.5. UTILIZATION OF SEXUAL MEDICATIONS/DEVISES: provides context for interpreting the sexual domain score of the EPIC questionnaire.
- 9.4. CRITERIA FOR DISEASE CONTROL: intervals will be measured from enrollment date.
 - 9.4.1. BIOCHEMICIAL DISEASE-FREE SURVIVAL (bDFS): is measured as time to PSA failure. While earlier reports of prostate cancer patients treated with radiotherapy have used the ASTRO consensus definition (ACD) of PSA failure, recent studies^{2,3,4} have suggested the "nadir+2" definition is a more sensitive and specific definition of biochemical failure. Indeed, a recent expert panel met in Phoenix⁵ and developed a consensus recommendation using the later definition. So that comparisons can be made with earlier literature, both definitions shall be used:

П

- 9.4.1.1.Phoenix definition: failure occurs when the PSA is 2 ng/ml more than the lowest PSA measurement before the current one, with no backdating. Administration of salvage therapy (hormones, surgery, etc...) will be considered failure.
- 9.4.1.2.Strict ASTRO Consensus Definition (ACD): failure is defined as three consecutive rises in post-treatment PSA, measured at the specified follow-up intervals. If three consecutive PSA rises occur during the first 2 years after treatment, followed by a non-hormonal induced PSA decline, this will not be considered a failure. Administration of salvage therapy (hormones, surgery, etc...) will be considered failure. Failure date is the midpoint between the dates of the last non-rising PSA and the first PSA rise.

9.4.2. CRITERIA FOR LOCAL FAILURE:.

Clinical evidence of local progression or recurrence: Clinical failure includes a palpable abnormality that has increased in size, failure of regression of a palpable abnormality by 2 years after treatment, or redevelopment of a prostate abnormality after complete response. Patients with a prostate abnormality compatible with local recurrence, or a PSA failure shall undergo a prostate biopsy. Histologic criteria for local failure is a positive prostate biopsy more than 2 years after treatment. Patients with a normal exam and no evidence of PSA failure shall be considered controlled locally. Patients with clinical failure and no biopsy are considered local failures. If a patient is locally controlled at the time of orchiectomy or androgen ablation, he is censored and considered "not evaluable" for further local control.

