11. STATISTICAL CONSIDERATIONS

- 11.1. OVERVIEW: The study's primary goals are to determine CyberKnife monotherapy efficacy and to evaluate the incidence of grade 3 or higher toxicity as stated in Section 2.0. Per RTOG/ECOG, acute toxicity will be defined as occurring within 90 days from completion of treatment. Late toxicity will be defined as occurring more than 90 days from completion of treatment. It is graded based upon Common Terminology Criteria for Adverse Events (CTCAE), v3.0., and RTOG/ECOG definitions (see appendix 5).
- 11.2. INTERIM ANALYSIS: An interim analysis was performed. The results below are based on an overall one-sided alpha of 0.05 and using the O'Brien-Fleming spendingfunction, and were calculated using nTerim (Statistical Solutions Ltd). The interim analysis is based on 4,512 months of follow-up, out of a total possible of 15,600 months (60 months* 260 Subjects). Hence the interim analysis is performed with approximately 29% of the total data possible for the final analysis. The final alpha must now be 0.04999. If the Z-score at the interim analysis exceeds 3.45701, then the trial could be stopped. If th Z-score doesn't exceed 3.45701, then the trial will continue through the primary assessment period of 5 years, where the P-value for success is at most .0499991.

	Look 1	Final Analysis- Look 2
proportion of information	0.29	1.0
Z-Score Boudary	3.45701	1.64575
Nominal Alpha	0.00027	0.049991
Incremental Alpha	0.00027	0.05

11.3. SAMPLE SIZE:

Primary Efficacy Endpoint and Hypothesis: 5-Year Biochemical Disease-Free Survival(bDFS) Among CyberKnife Treated Patients

bDFS is the primary efficacy outcome for the study. The proportion of patients disease-free within 5 years of the initial procedure is the rate of interest. The null and alternative hypotheses are as follows:

$$H_0: \pi < 90\%$$

 $H_1: \pi \ge 90\%$

 π • • is the expected proportion of CyberKnife treated patients bDFS at 5 years. The CyberKnife procedure is considered to be effective if this study's result verifies that the lower limit of the one-sided 95% confidence interval for π is not below 90%. Statistical Sample Size Derivation

Primary Efficacy Objective

We calculate the CyberKnife Treatment Group sample size, N, required to test the null hypothesis that the rate in the Treatment Group is less than 90%, against the one-sided alternative hypothesis that the rate is at least 90%...

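### If ASTRO decides the primary test, failures that the plan dates to year 5 are largely unconfirmed at a 5-year analysis, so bDFS is biased upward against the 90% bar

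*Combined protocol and SAP*

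**What the plan says.** - **ASTRO failure (9.4.1.2):** "failure is defined as three consecutive rises in post-treatment PSA, measured at the specified follow-up intervals". It is then backdated: "Failure date is the midpoint between the dates of the last non-rising PSA and the first PSA rise". There is one other route to failure: "Administration of salvage therapy (hormones, surgery, etc...) will be considered failure".
- **Phoenix failure (9.4.1.1):** a PSA 2 ng/ml above the lowest earlier value, "with no backdating". The same salvage rule applies.
- **PSA schedule (9.1.4):** "At 3, 6, 12, 18, and 24 month (+/- 2 wks) intervals (and every 6 months thereafter, through year 5"; then "After the 5 year follow-up patients will be seen yearly through year 10".
- **Clock (9.4):** "intervals will be measured from enrollment date". Section 6.2 allows up to 90 days from registration to the first fraction. Section 11.3 instead counts 5 years from the initial procedure.
- **Primary test (11.3, 11.4.1):** the observed proportion free of biochemical failure within 5 years is put into a one-sided 95% score limit L. The treatment is declared effective if L is not below 90%.
- **Timing (11.2):** if not stopped at the interim look, "the trial will continue through the primary assessment period of 5 years". Section 2 describes follow-up to 10 years as additional data for descriptive analysis.
- **Which definition decides:** section 2 names both Phoenix and ASTRO for the primary endpoint. Neither section 2 nor section 11 says which one enters the test.

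**The concern.** Backdating places a failure before the visit at which it can be recognised, and the gap widens when visits become yearly after month 60. At a 5-year analysis the plan would have dated some failures inside the 5-year window without yet being able to call them. No rule covers a man with one or two unresolved rises at month 60, so he enters the simple proportion as disease-free. The error runs in one direction, towards declaring efficacy, and the test is against a fixed 90% with a narrow margin. A shift of one or two percentage points therefore changes the error rate of the test materially.

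**Working it through.** **1. The plan's own sample size.** Formula 1 in 11.3 with π₁ = 0.945, π₀ = 0.90, z = 0.84 and 1.645:

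[0.84 × √(0.945 × 0.055) + 1.645 × √(0.90 × 0.10)]² / 0.045² = 231.7, so 232; and 232 / 0.92 = 252.2, so 253.

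Both stated figures are reproduced.

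**2. The success rule.** From L in 11.4.1 at n = 232, 216 successes give L = 0.898 and 217 give L = 0.903, so success needs at least 217. By exact binomial, the chance of success is 4.0% at a true 90% and 79.0% at 94.5%. At n = 253 the rule is at least 236, with 4.5% at a true 90%.

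**3. When each ASTRO failure can be called** (months after treatment):

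| Last non-rising PSA | First rise | Dated | Third rise seen |
|---|---|---|---|
| 36 | 42 | 39 | 54 |
| 42 | 48 | 45 | 60 |
| 48 | 54 | 51 | 72 |
| 54 | 60 | 57 | 84 |

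No PSA-defined ASTRO failure with onset in months 48 to 60 can be called by month 60.

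**4. Size of the bias.** The documents give no failure-time pattern for this trial. I assume a constant failure rate, which the protocol itself uses under Table 1 to project one series to 5 years. Then S(t) = S(60)^(t/60). At a true S(60) = 0.90:

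- S(48) = 0.90^0.8 = 0.9192 and S(54) = 0.90^0.9 = 0.9095.
- Hidden at a hard month-60 cut: 0.9192 − 0.9000 = 1.9 points, about 4.4 of 232 men.

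**5. If all data held when the last patient reaches month 60 are used.** Assume uniform accrual over the 29 months in 11.3.1. Then (29 − 12)/29 = 59% have a month-72 PSA and (29 − 24)/29 = 17% a month-84 PSA. The hidden part is 0.0096 × (1 − 0.586) + 0.0095 × (1 − 0.172) = 1.2 points.

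**6. Chance of declaring success at a true 90%, N = 232** (exact binomial, at least 217):

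| Scenario | Rate the test sees | Chance of success |
|---|---|---|
| No hidden failures | 90.0% | 4.0% |
| Hard month-60 cut, no salvage | 91.9% | 22.0% |
| Hard cut, salvage reveals 25% of hidden failures | 91.4% | 15.2% |
| Hard cut, salvage reveals 50% | 91.0% | 10.1% |
| Month-72 data for everyone, no salvage | 91.0% | 10.1% |
| All held data (step 5), no salvage | 91.2% | 12.3% |
| All held data, salvage reveals 50% | 90.6% | 7.2% |

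The salvage shares are assumptions; the documents give no figure.

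**7. Other sensitivities (hard cut, no salvage).**

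- At a true 89%: 1.3% becomes 11.4%.
- At the design rate of 94.5%: 79.0% becomes 94.6%.
- At N = 253 and a true 90%: 4.5% becomes 25.4%.
- If the share of 5-year failures that is hidden is 10%, 20% or 30%, whatever the failure-time pattern: 10.5%, 23.4% or 43.9% at a true 90%, N = 232.
- Clock from enrollment with the full 3-month lag: onset after month 51 is hidden, 0.90^(51/60) − 0.90 = 1.4 points, giving 15.2%.

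**The case against.** **The estimand may be status at the 5-year visit.** The primary measure is a simple proportion, not a Kaplan-Meier estimate. If being disease-free within 5 years means not having met the ASTRO definition by the 5-year assessment, a man with one rise at month 60 has not failed and nothing is hidden. The plan does not exclude this reading. But 9.4.1.2 gives every ASTRO failure a date, and for these men that date lies before month 60. The status reading would leave the dating rule with no role in the primary test.

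**The data cut is not fixed.** A reader might infer from 11.2 that data stop at month 60 for each patient, and hence that year-5 failures cannot be seen at all. The text gives a follow-up horizon, not a database lock. Sections 2 and 11.2 lean towards month 60, but they do not forbid using later PSAs to classify failures dated earlier. Salvage therapy also counts as failure without three rises. Both points stand: they take the figure below 22%, but in the scenarios examined not back to 5%.

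**The literature shares the delay.** The 94% prediction rests on ASTRO-based series with short follow-up, and those rates may be inflated in the same way. That bears on the descriptive comparison. It does not restore the error rate of a test against a fixed 90%.

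**Phoenix may be the deciding definition.** If so, the primary test is unaffected. The plan does not say so, and its projected rate is ASTRO-based because, by its own account, Phoenix results were too few.

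**Conclusion.** The mechanism and its upward direction follow from the plan's own failure definition, visit schedule and estimator. If ASTRO decides the primary test and backdated failures count from their assigned date, the chance of declaring success at a true 90% with N=232 rises from 4.0% to between about 7% (all data held when the last patient reaches month 60, salvage revealing half of the hidden failures) and 22% (hard month-60 cut, no salvage). This range assumes a constant failure rate; the size depends on that assumption, the direction does not.

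Three stronger readings are tempting and not supported. The 22% is the upper end of this range, not an established error rate for the trial. It is not shown that the primary result is biased, because the deciding definition is open and Phoenix is unaffected. And the sample size calculation is not at fault: it reproduces.

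**What to change.** State in 11.3 and 11.4.1 that the Phoenix definition decides the 5-year test against the 90% bar. Report the backdated 5-year ASTRO rate as the literature comparison, computed only once the month-72 and month-84 PSAs are in. Limit any earlier ASTRO estimate to dates with full confirmation, about month 48, and say how men with one or two unresolved rises are handled.

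Dating the ASTRO failure at the third rise is not a remedy. The men whose third rise falls by month 60 are the same men already counted under backdating, so the observed proportion and the chance of passing at a month-60 cut do not change.

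The cost is wording: the later PSAs are already scheduled, so no visits are added. The ASTRO comparison arrives up to 2 years later. The 90% bar was set alongside ASTRO-based literature because few Phoenix results existed, so the amendment should say that 90% is being kept for Phoenix and why. As 11.2 reports that an interim analysis has been done, the amendment should also record that the definition was chosen without reference to results by definition.
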